#### **4.3 Risk of Harm**

There is less than minimal risk involved. The VR experiments are non-invasive and pose no obvious risk. Transient fatigue of the hand and arm are possible, but this risk is not greater than that posed by normal daily activities following a stroke.

#### **4.4 Potential for Benefit**

The benefits of taking part in this study may be: Patient may regain better use of their hand and arm. However, it is possible that patients might receive no direct personal benefit from taking part in this study.

### **5. Data Handling and Statistical Analysis**

All efforts will be made to keep subjects' personal information confidential. All subject names will be removed from the data and the data will be tagged using a coded ID number.

Demographic, clinical outcome and survey data will first be recorded on paper. All kinematic and computerized performance data will be collected on computer. These computer files will be identified by the coded subject ID number. All data will be transferred to an Excel spreadsheet with subjects identified by this same ID number. Spreadsheets will be stored on a drive that is password protected. Data will only be accessible to study staff and will be retained for seven years. The link between subject identity and subject ID number will be destroyed when data collection is completed.

Our primary outcome measures will be the WMFT (Aim 2) and the duration of motor activity (measure of compliance, Aim 1). The primary outcome measures and all secondary outcome measures described above will be subjected to a repeated measured analysis of variance, with between-group factors Therapy Type (Virtual Simulations (VS), Standard Exercise (SE)) and within-group factor Test (Before, Post, One Month retention, Six Months Retention). Our post-hoc analyses of the Therapy Type by Test interaction effects will focus on the Month 1 versus Month 6 comparison. We will be quantifying training effects by comparing group means as well as by percent change in performance, and by comparing the recovery curves obtained from Tests 1-4. All clinical outcomes used are well established measures of upper extremity functional recovery with published minimum clinically important differences which we will use to evaluate the significance of our findings.

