## Home Based Virtual Rehabilitation for upper extremity

**Title of Project:**

**Principal Investigator:**

**[name] PT PhD**

**Funding Source(s):**

**NIDILRR #90RE5021-01-00**

**NIH NICHD #1R15HD095403-01A1**

### 1. Purpose/Specific Aims

The overarching aim of this study is to provide a mechanism for patients to engage in progressive motor practice for a meaningful time period. We aim to improve on the positive outcomes found in our work on patients in the chronic phase and the pilot work being done on patients in the acute in-patient phase post stroke to determine whether we can further improve functional recovery using a home based system.

Aim 1: Evaluate compliance with Home-Based Virtually Simulated hand/arm gaming activities and two computer game groups, one with motivation enhanced (ME) simulations and one with non-enhanced (MnE) versions, as compared to compliance with Standard hand/arm home Exercises (HBSE). Hypothesis: Participants in the ME and MnE group will show significant compliance as compared to the control group (HBSE) and the ME group will be superior to the MnE group.

Primary Outcome Measures: For the HBVS group, 1) time on task will be measured by the daily computer file time stamp and 2) amount of moving time will be measured by the actual movement time recorded by the games. For the computer games groups 1) time on task will be measured by recording start and stop time of practice in a notebook and 2) amount of moving time will be measured by commercially available activity monitors.

Aim 2: Evaluate the effectiveness of home-based virtually simulated hand/arm gaming activities (HBVS) for individuals with stroke as compared to a program of standard hand/arm home exercises (HBSE). Hypothesis: Participants completing HBVS training will exhibit significantly improved clinical, kinematic and neurophysiological outcomes as compared to the control group (HBSE).

Primary Outcome Measures for Aim 2: Wolf Motor Function Test, Upper Extremity Fugl-Meyer Assessment of Sensorimotor Recovery after Stroke, Action Research Arm Test, Perception of System Questionnaire, the Stroke Impact Scale, Kinematics, Cortical mapping.

Aim 3: Evaluate the impact of the motivation enhancements designed into computer games to provide a more enjoyable training experience. Hypothesis: Enjoyment of the games will be a more valid predictor of compliance than personal factors.

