### ***3.3 Sample Size Justification***

In this pilot study we will seek sufficient power to detect a clinically significant difference in the Wolf score changes in these two pre-planned, primary comparisons. To evaluate these effects of training, we will assume a power level of .8 and a significance level of 0.05. With presumed correlation among repeated measures of 0.1 and effect size of 0.3, we will need a sample size of 25 subjects in each of the three groups (HBVS, ME and MnE) to observe a significant effect for the first comparison (G\*Power, version 3.1.5). Although we will screen for patients with homogeneous impairments, by its nature stroke is an extremely variable condition. Due to possible subject attrition, we will use a total of 30 subjects in each of the two groups.

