### **4.2 Dependent Variables or Outcome Measures**

All subjects will come to our lab and complete a quality of life questionnaire (Stroke Impact Scale) [4] and undergo clinical and kinematic testing immediately pre and post training as well as at 1 and 6 months post training. Additionally they will complete a perception of the system questionnaire [5] after training is completed.

Clinical Measures. The main clinical outcome will be the Wolf Motor Function Test [6] because it is a balanced test of arm and hand use [7, 8]. The secondary measures will be the Upper Extremity Fugl-Meyer Assessment[9], the Action Research Arm test[10], and Kinematic/Kinetic Measures. To explore the mechanism of improvement, changes in kinematics and kinetics of the hand and arm will be used to elucidate recovery of impairment. Two types of kinematic data will be collected; 1) data obtained from the patient's daily performance during the training and 2) data collected during the 4 testing

periods. Data obtained from the patient's daily gaming performance during the training will include duration of motor activity, hand opening and closing range of motion, pronation and supination range of motion, maximum fractionation (a measure of finger individuation), hand opening velocity, hand trajectory smoothness, game duration and game score.

Data collected during the 4 testing periods includes computer-based outcome measures and the Real-World Reach to Grasp Test. There are four computer based outcome measures in this data set. 1) Maximum Finger Opening is collected using a CyberGlove™ (Immersion, USA) (2) Pinch Force Tracking Error measures the ability to control active finger extension and flexion to modulate their pinch grip force to control a cursor to track a sine wave. (3) Maximum Pinch Force is measured as the maximum force a subject can exert on a force sensor held between their paretic thumb and index finger and, (4) Figure 8 Tracking Error measures forearm and shoulder control needed to trace a horizontal figure 8 shape while the arm is in a supported horizontal position[11] (5) Max finger extension and abduction (collected using a CyberGlove) (6)Maximum supination with hand open, measured with an Optitrack system. (7) Maximum pronation with hand open, measured with an Optitrack system (8) Maximum MCP flexion with PIP and DIP extension measured with an Optitrack system.

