targeted to train movement of their shoulder, elbow and fingers. The physical therapist will set up the apparatus in their home and visit them once or twice in the first week to train them how to use the system and how to play the games. After this training period they will then continue to practice in their homes independently with on-line support from the therapist and in-person or on-line assistance from the study-engineer as needed. Both groups will be instructed to perform all three of the simulations assigned to them for at least twenty minutes, daily for twelve weeks.

**Figure 5.** Left: Patient home system setup with the passive arm support, hand tracking device and computer. Right: Patient is able to talk to and see therapist (lower left corner) and while playing games, patient's game screen is shared with therapist at the same time as well.

(career score) on that simulation, and the top ten career scores for the entire program (including other subjects). When users achieve a

The enhanced motivation (EM) group will train using three simulations (See Table 2). These simulations will all provide the user with eight to twelve levels of gradually increasing difficulty and complexity. There is a screen announcing each level change and the graphics for each new level change substantially. Scoring opportunities increase at each new level as well. When a simulation is completed, for the day, a leaderboard displays the user's score for the day, their total points scored for the entire training period

milestone career score (1 million points, two million points, three million points), they will have an opportunity to choose a new avatar for future play. This opportunity is provided at the beginning of gameplay.

The unenhanced control (UC) group will perform the same three simulations. Difficulty will increase utilizing an adaptive control algorithm that increases difficulty based on performance. Difficulty changes are extremely incremental making them imperceptible for most subjects. Graphics and scoring will not change as difficulty level changes. Total score for the day will be displayed after each simulation for the day is completed, but no leaderboard displaying past performances, career scores or the career scores of other subjects will be displayed. UC subjects will use the same avatars for the entire experiment.

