these steps: 1) A trained interviewer will ask open-ended questions in telephone interviews, allowing participants to reflect on and describe their experiences. 2) Investigators will read participants' narratives to develop a general sense of the subjects' experiences and attitudes toward the rehabilitation program. 3) Investigators will identify emerging narrative themes in participants' experiences and attitudes toward the program. 4) Finally, an iterative coding process will be used to refine initial findings and synthesize these themes.

*Statistical Analysis:* (See Table 5 for a summary of all planned comparisons.) Linear regression will be used to evaluate the effects of IMI (From Data Collection 1) on total time (Collected during training sessions).

**Aim 3: To test the impact of motivation enhanced, game-based interventions on the effectiveness of a telerehabilitation exercise program in persons with strokes.**

*Rationale:* Studies of clinic based interventions targeting hand function in persons with stroke have produced measurable changes in hand function that do not substantially reduce hand related disability. Study of a long term, home based program emphasizing adherence will inform the development of sustainable alternatives to costly clinic based interventions that fall short of the ultimate goal of rehabilitation.

*Hypothesis:* We predict that subjects in the ME group will demonstrate larger improvements in hand function as measured by the Action Research Arm Test (ARAT) than those performing UC interventions. We further predict that subjects in the ME group will demonstrate larger reductions in impairment and larger improvements in measures of motor control and quality of life than UC group subjects.

*Subjects:* The same subjects will be utilized for Aims 1-3.

*Outcome Measures:* (Please see Table 4 for the full listing and description of the proposed clinical and quality of life measures.) A trained RA, blinded to group assignment will collect all outcome measures described in Table 4 immediately prior to training, immediately after training and 3 months after training (Data Collections 1 and 2). The RA will be blinded to previous test scores during post testing and retention testing.

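### The four-test repeated-measures ANOVA does not fit duration of motor activity, the primary compliance outcome, and no rule says how a subject who stops practising is scored

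*Protocol*

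**What the plan says.** Protocol Section 5 names two primary outcomes: "Our primary outcome measures will be the WMFT (Aim 2) and the duration of motor activity (measure of compliance, Aim 1". It then says that "The primary outcome measures and all secondary outcome measures described above will be subjected to a repeated measured analysis of variance", with "within-group factor Test (Before, Post, One Month retention, Six Months Retention" as the repeated factor. No separate analysis is given for compliance.

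Protocol Section 4.2 describes when duration is obtained: the patient's "daily gaming performance during the training will include duration of motor activity". It is not among the measures that Section 4.2 lists for the four testing periods.

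Recording differs by group. In Protocol Section 1, Aim 1, for the HBVS group "time on task will be measured by the daily computer file time stamp". For what that section calls the computer games groups, the sources are a notebook and activity monitors.

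Attrition appears once, in Protocol Section 3.3, where 25 per group becomes 30: "Due to possible subject attrition, we will use a total of 30 subjects in each of the two groups".

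In the SAP, Treatment Protocol, subjects are told to practise "for at least twenty minutes, daily for twelve weeks". SAP Table 4 lists total intervention time as recorded by the system. The Aim 2 analysis reads: "Linear regression will be used to evaluate the effects of IMI (From Data Collection 1) on total time (Collected during training sessions". Protocol Section 3.1 instead allows training of 3 to 12 months.

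**The concern.** Aim 1 of the Protocol asks whether the games keep people practising. A subject who stops has an unknown later Wolf score, but does not have unknown later practice: it is zero from that day. Stopping is part of the outcome.

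Protocol Section 5 does not say whether such a subject counts with the minutes accrued and zeros afterwards, with minutes per day until leaving, or as missing. These scores answer different questions and can disagree in sign. The one model that is named has no natural place for a quantity gathered only during training, and in its classical form it needs every test from every subject. An analyst who tries to follow Section 5 must improvise, possibly after seeing the data, on a primary outcome. One obvious improvisation keeps only subjects with complete tests, and a benefit that works by preventing quitting would then not be seen.

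**Working it through.** **1. The plan's own figures.** Section 3.3 uses power 0.8, alpha 0.05, effect size 0.3 (read as Cohen's f) and correlation 0.1. For a between-groups effect with 2 groups and 2 measurements, lambda = f² × N × m / (1 + (m − 1) × rho) = 0.09 × 50 × 2 / 1.1 = 8.18. Power is 0.800 at N = 50, which reproduces 25 per group. That calculation is for the Wolf score; there is none for compliance. The step from 25 to 30 implies attrition of 1 − 25/30 = 16.7%. No rate is stated.

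**2. Does the model fit?** The ANOVA needs a value at Before, Post, 1 month and 6 months. Duration accrues between Before and Post. Neither Section 4.2 nor Section 5 describes a value before training or at retention, or a way of assigning training minutes to a test. The model cannot be fitted to duration as written, for any subject.

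**3. What would excluding stoppers do?** Let D be a subject's total over the full window at the usual daily rate, p the proportion who stop, and s the mean fraction of the window that stoppers complete. If stopping is unrelated to daily rate:

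- mean with everyone scored = D × [1 − p × (1 − s)]
- mean among completers = D

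Inputs from the SAP: 84 days × 20 min = 1680 min. This is a minimum, and it reads the twenty minutes as a daily total. All other inputs are assumptions.

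*Set A.* Mean practice 60%, so D = 0.6 × 1680 = 1008 min in both arms; stopping uniform over 84 days, so s = 0.5; SD 420 min.

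- 10% vs 23.3% stop (average 16.7%): 1008 × 0.5 × 0.133 = 67 min with everyone scored (68 by simulation); 0 among completers.
- 5% vs 28.3% stop: 1008 × 0.5 × 0.233 = 117 min (118 by simulation); 0 among completers.

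*Set B.* Stopping uniform over the first half of the window, so s = 0.25; SD 8 min/day.

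| Stopping | Min/day while training | Everyone scored | Completers only |
|---|---|---|---|
| 10% vs 40% | 20 vs 20 | 28 × 0.925 − 28 × 0.70 = 6.3 h | 28 − 28 = 0 h |
| 16.7% in both arms | 22 vs 18 | (30.8 − 25.2) × 0.875 = 4.9 h | 5.6 h |
| 40% vs 10% | 22 vs 18 | 30.8 × 0.70 − 25.2 × 0.925 = −1.8 h | +5.6 h |

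Unequal stopping can erase the difference (first row) or reverse it (third). With equal stopping (second row) it survives and is slightly larger among completers.

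**4. Would the trial's conclusion change?** With 30 per arm and a two-sided t test at 0.05, power with everyone scored is about 9% for the 68-minute difference, 17% for 118 minutes and 45% for 6.3 hours, against about 5% among completers in each case. At the milder stopping rates the trial would usually miss the difference either way. The estimate is still of a different quantity.

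**The case against.** The strongest reply is that nothing in the Protocol says anyone is dropped. That is correct. Exclusion is a default of the classical method, and it arises only once duration has been forced into a model that does not fit it.

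Stopping practice and missing a test are also different events. A subject may quit the games and still attend the tests (the retention visits are paid), or train fully and miss month 6. The implied 16.7% is an attrition allowance in a Wolf-score calculation, not a rate of stopping training. This stands, so 16.7% only sets the scale of an illustration.

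The zero among completers in Set A follows from assuming equal daily practice in both arms. The examples also put the SAP's 84 days and twenty minutes into a two-arm comparison with the Protocol's 30 per group, while the SAP describes 30 subjects in total, all playing games. Both points stand.

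A reader might infer that the SAP regression of total time on IMI also loses slope and power by leaving out early stoppers. The documents do not support that. Total time is recorded by the system, an early stopper's accrued minutes are available, and the regression needs one total per subject, with no stated exclusion. SAP Table 5 and the Aim 3 analysis are not in the available text, so a scoring rule there cannot be ruled out.

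**Conclusion.** The concern holds in a limited form. Protocol Section 5 assigns a primary compliance outcome to a model that does not fit it, and gives no score for subjects who stop. The mismatch rests on the text alone.

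The bias from a completers-only analysis is conditional: it requires that the analyst falls back on complete cases and that stopping differs between arms. Under the Set A assumptions it is about 68 of 1680 prescribed minutes (4%) at 10% vs 23% stopping, and under Set B a 6.3-hour difference disappears at 10% vs 40%. The documents do not show that a real difference will vanish, nor that the plan intends to exclude anyone. The change is worth making because it is cheap and settles a primary analysis before data are seen.

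**What to change.** First reconcile the training length in Protocol Section 3.1 with that in the SAP Treatment Protocol, so that each subject has a defined assigned window.

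Then, in Protocol Section 5:

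- Take duration of motor activity out of the four-test ANOVA.
- Compute one score for every randomised subject: total minutes, or mean minutes per assigned day, over the assigned window. Count zero for each day without practice, including all days after stopping or withdrawal.
- Compare the arms once on that score.
- Report the proportion who stop in each arm, and give minutes while still training as a supportive analysis.
- Treat an unreturned notebook or activity monitor as a missing record, with a sensitivity analysis, and not as zero practice.

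In SAP Aim 2, state that total time includes the accrued minutes of subjects who stop early.

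The cost is wording; no new visit or measurement is needed. There are two downsides. The totals will be skewed with a low tail, so a rank-based or robust check may be needed. Recording methods that differ by group will still limit comparability, whichever score is used.

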### ***3.1. Duration of Study***

Each subject will perform a pre-study evaluation, train using one of the protocols for three to twelve months, perform a post study evaluation as well as one and six month retention evaluations.

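### The four-test repeated-measures ANOVA for the WMFT by default drops anyone with a missed test; a mixed model on all observed tests would avoid the lost data and the possible bias

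*Protocol*

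**What the plan says.** Protocol Section 5 names two primary outcomes, the WMFT and the duration of motor activity. It says that these and all secondary outcomes "will be subjected to a repeated measured analysis of variance". The between-subject factor is therapy type, with two levels (virtual simulations and standard exercise). The other factor is the "within-group factor Test (Before, Post, One Month retention, Six Months Retention", so there are four scores per subject.

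Protocol Section 3.1 has subjects "train using one of the protocols for three to twelve months, perform a post study evaluation as well as one and six month retention evaluations". From the Before test to the last test is therefore about 9 to 18 months.

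Protocol Section 3.3 foresees losses: "Due to possible subject attrition, we will use a total of 30 subjects in each of the two groups". It gives no rate.

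The protocol states no analysis population, no method for missed tests and no sensitivity analysis. It also states no rule that subjects with a missed test are to be removed.

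**The concern.** A classical repeated-measures ANOVA needs a complete row of scores for each subject, and standard procedures drop any subject with a gap. Nothing in Section 5 overrides that default. A subject who trains, attends the post test and misses the six-month visit would then be lost from the post-training comparison as well, although that score was observed.

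Two things are at stake. One is precision. The other, and the more important, is that the WMFT comparison would rest on those who stayed for every visit. If the reasons for leaving are related to progress and the losses differ between arms, the estimated effect is shifted, and the shift can go either way. Unequal losses are plausible, because the hypothesis of Protocol Aim 1 is that compliance differs between the groups.

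**Working it through.** **1. The plan's own figure.** Inputs from Protocol Section 3.3: power 0.80 and alpha 0.05 ("we will assume a power level of .8 and a significance level of 0.05"), and "With presumed correlation among repeated measures of 0.1 and effect size of 0.3". I read the effect size as Cohen's f (assumption). For the between-group test in a repeated-measures ANOVA with k groups of n, m measurements and N = kn:

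λ = f² N m / (1 + (m − 1)ρ), with k − 1 and N − k degrees of freedom.

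With k = 2, m = 2, n = 25: λ = 0.09 × 50 × 2 / 1.1 = 8.18, power 0.800. The stated 25 is reproduced with two groups and two measurements. It is not reproduced with three groups or with four tests: two groups and four tests give 16 on the same formula. Section 3.3 speaks of three groups, then of two, and Section 5 plans four tests; these passages need to be reconciled separately.

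**2. Attrition and power.** Implied attrition is (30 − 25)/30 = 16.7%.

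- 25 complete per group: power 0.800.
- All 30 contributing fully: λ = 0.09 × 60 × 2 / 1.1 = 9.82, power 0.869. This is the ceiling on what partial data could add.
- If one-sixth missed each of the three later tests independently (assumption): 30 × (5/6)³ = 17.4 complete. With 17, λ = 5.56 and power is about 0.63.
- At a test attended by all 30, using only 25 raises the standard error by √(30/25) = 1.095, about 9.5%.

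**3. Bias.** Assumptions: 30 per arm; unit SD; equal correlation ρ between tests; true effect 0.60 SD at all three later tests and no change in control; about one-sixth lost overall, all after the post test; leaving depends on the subject's observed Before-to-Post change plus independent noise. The analysis compared is change from Before in complete cases.

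*Size of the shift.* If a share p of an arm leaves, taken from the low end of (change + noise of SD 1), mean change among those who stay rises by:

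- post test: 2(1 − ρ) h / √(2(1 − ρ) + 1)
- one or six months: (1 − ρ) h / √(2(1 − ρ) + 1), half as much

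Here h = φ(z)/(1 − p), where z is the p-quantile of the standard normal. For p = 1/3, h = 0.545; for p = 1/6, h = 0.300.

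*Equal shares from each arm.* Both arms shift alike and the difference is unbiased. Simulation gives 0.59 to 0.61 for ρ from 0.1 to 0.8. Within-group change is still inflated. At ρ = 0.7 the post-test shift is 0.6 × 0.300 / √1.6 = 0.14, so control shows 0.14 instead of 0 and treatment 0.74 instead of 0.60. A simulation with a tighter link between response and leaving gave 0.17 and 0.78.

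*One common rule in both arms.* The chance of leaving falls with the subject's own change. Fewer treated subjects then do poorly, so control loses more. At the post test the complete-case effect is about 0.54 to 0.55 with a shallow rule and 0.46 to 0.48 with a steep one. In the steep case at ρ = 0.7, losses are about 24% in control and 10% in treatment.

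*All losses in one arm* (10 of its 30), six-month test, 4,000 simulated trials per cell:

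| ρ | Shift by formula | Complete-case, losses in control | Complete-case, losses in treatment | Likelihood, all observed data |
|---|---|---|---|---|
| 0.1 | 0.29 | 0.30 | 0.88 | 0.59 |
| 0.5 | 0.19 | 0.42 | 0.79 | 0.60 |
| 0.8 | 0.09 | 0.50 | 0.69 | 0.59 to 0.60 |

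By the formula the post-test shift is twice this. At ρ = 0.1 it is 2 × 0.293 = 0.587, so the complete-case post-test effect would run from 0.60 − 0.587 = 0.01 to 0.60 + 0.587 = 1.19.

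**The case against.** The strongest reply is that the protocol leaves the handling of missed tests unstated and prescribes nothing wrong. That is true of the wording. Listwise deletion is the default of the named method, not a written rule, and Section 5 also plans group means, percent change and recovery curves, which need not use complete rows. But the inferential method is named, its default is known, and no text overrides it.

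Four stronger readings are tempting, and the documents do not support them.

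- *The plan expects 17% attrition.* Section 3.3 calls attrition possible; 16.7% follows only from 25 and 30.
- *The trial loses its power.* The 30 per group covers loss down to 25 complete cases. Power falls below 0.80 only if more than one-sixth are incomplete.
- *Poor responders leaving biases the comparison in itself.* With equal shares lost from each arm there is no between-arm bias. The losses must differ.
- *The effect will be understated.* It is overstated if losses fall mainly in the treatment arm. The documents give no dropout by arm, so the direction is unknown.

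Protocol Section 3.5.5 also pays subjects at each retention test, which may limit losses. The SAP text reviewed stops before an analysis for its Aim 3 and lacks the table of planned comparisons that it cites, so nothing can be concluded about missing data there.

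Finally, the mixed model's good showing depends on losses being explained by observed scores. That stands, and is why the fix includes a sensitivity analysis.

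**Conclusion.** The point holds for the WMFT and the other outcomes measured at the four test sessions. The named method would by default set aside observed scores, and the attrition allowance protects power but not the validity of the comparison. The effect can be shifted in either direction when losses differ between arms. With a true effect of 0.60 SD, the shift is nil with balanced losses, about 0.05 to 0.14 SD at the post test under one common dropout rule, and up to about 0.30 SD at six months (twice that at the post test) in the extreme case of all losses in one arm. Within-group readings, which Section 5 also plans to judge against published minimum clinically important differences, are inflated even when losses are balanced.

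These sizes rest on assumptions that the documents do not supply: the effect, equal correlations, the dropout rule and losses only after the post test. They show what can happen and are not a forecast. The largest shift arises at ρ = 0.1, the plan's own presumed correlation; at 0.8 it is about a third of that. The change is worth making before the data are analysed.

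**What to change.** In Protocol Section 5, for the WMFT and the other test-session outcomes:

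1. Replace the ANOVA with a likelihood-based linear mixed model with arm, test and arm-by-test, and an unstructured covariance across tests, using all observed tests from every randomised subject.
2. State how the Before score enters: either as a covariate, with the three later tests as outcomes, or as one of four levels of Test. It must not be both.
3. Take the arm contrast at each test from this model. The Month 1 versus Month 6 comparison comes from the same fit.
4. Add one sensitivity analysis for losses not missing at random, for example by shifting the imputed missing scores over a stated range, separately by arm.
5. Report the number with each test by arm, so that unequal loss can be seen.

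This does not apply to the duration of motor activity. Protocol Section 4.2 records it during training, so the four-test structure does not fit it and it needs its own analysis statement.

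The cost is a rewritten paragraph and a little more analysis work, with no new subjects, visits or data. The downside is that the main model assumes losses depend only on observed scores; item 4 tests that assumption but cannot remove it.

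### Protocol Section 5 analyses the Aim 1 primary outcome, duration of motor activity, across four test visits although it is collected only during training; Section 5 also has no ME versus MnE term

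*Protocol*

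**What the plan says.** Protocol Section 5 states: "Our primary outcome measures will be the WMFT (Aim 2) and the duration of motor activity (measure of compliance, Aim 1". It then assigns the primary and all secondary outcomes to one repeated-measures ANOVA, with "between-group factors Therapy Type (Virtual Simulations (VS), Standard Exercise (SE)) and within-group factor Test (Before, Post, One Month retention, Six Months Retention". No exception is made for compliance. Post-hoc work on the interaction "will focus on the Month 1 versus Month 6 comparison".

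Protocol Section 4.2 separates the kinematic data into two types: data from daily performance in training, and data from the four testing periods. On the first it says that "daily gaming performance during the training will include duration of motor activity". The variable does not appear in the list for the testing periods. Those periods are fixed by the statement that subjects have "clinical and kinematic testing immediately pre and post training as well as at 1 and 6 months post training".

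Protocol Section 1, Aim 1, predicts better compliance in both game groups than with standard exercise (HBSE), and also that "the ME group will be superior to the MnE group". On instruments, it says for HBVS that "amount of moving time will be measured by the actual movement time recorded by the games", and for the computer game groups that "amount of moving time will be measured by commercially available activity monitors".

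The only adherence model in the visible SAP text (Aim 2, Statistical Analysis) regresses total time on the Intrinsic Motivation Inventory score. The SAP refers to a Table 5 for all planned comparisons; that table is not in the text available.

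**The concern.** A four-visit ANOVA suits a measure such as the Wolf Motor Function Test, which is repeated at each visit. Duration of motor activity is a quantity of training. A subject has no training time before training starts, and no document describes collecting it at the retention visits. Applied to this outcome, most of the stated model has nothing to estimate, including the one post-hoc comparison that the plan singles out.

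Separately, Therapy Type has two levels, VS and SE. ME and MnE are both game groups, so a VS versus SE factor either pools them or leaves them out. It cannot show whether one is superior to the other.

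What is at stake is pre-specification of one of two primary outcomes. If the written analysis does not fit, someone must later choose the summary (total, weekly or per day), the handling of early stopping and the contrast, possibly with the data in view.

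**Working it through.** The documents state no figure for the compliance analysis that could be reproduced; the sample size in Protocol Section 3.3 is built on the Wolf score. The check is a count of estimable terms and a comparison of sections.

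**1. Which Test levels can hold a value** (levels from Section 5, collection times from Section 4.2)

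| Test level | Timing | Duration of motor activity |
|---|---|---|
| Before | before training | none |
| Post | just after training | possible, if the training total is entered here |
| One month | after training | none |
| Six months | after training | none |

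Usable levels: at most 1 of 4.

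**2. Degrees of freedom**, with g levels of Therapy Type and t levels of Test

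- Test, t − 1: as written 4 − 1 = 3; with one usable level 1 − 1 = 0.
- Therapy Type by Test, (g − 1)(t − 1): as written (2 − 1)(4 − 1) = 3; with one usable level (2 − 1)(1 − 1) = 0.
- Therapy Type, g − 1: 2 − 1 = 1 in both cases. This term survives if the outcome is recorded in both groups.

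**3. The named post-hoc comparison.** It needs values at one month and at six months. Levels with data: 0 of 2.

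**4. ME versus MnE.** One degree of freedom for Therapy Type is used up by VS versus SE. No other between-group factor is named, so Section 5 leaves none for a difference between two game groups. The SAP's adherence regression has no arm term in the visible text.

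**5. Is the outcome recorded in both groups?** Set side by side:

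- Section 1, HBVS: file time stamps for time on task; movement time from the games.
- Section 1, computer game groups: notebook start and stop times; activity monitors for moving time.
- Section 1, HBSE: no instrument named.
- Section 4.2: duration of motor activity comes from gaming data, with no separate source for the exercise group.

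The game groups thus have two different sources for the same quantity, and the exercise group has no stated source. The notebook and monitor sentence may have been meant for the exercise group, but the text does not say so.

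**6. Which arms exist?** Protocol Section 3 refers to treatment and control groups. Section 3.3 lists three groups (HBVS, ME, MnE) and then speaks of two. Sections 4.1 and 4.1.1.2 describe two game groups and a video exercise group. The SAP (Treatment Protocol; Subjects) describes 30 subjects in two groups, both using the game system. Whether HBSE is randomised together with ME and MnE cannot be determined. Under the SAP's design both arms would be VS, and the surviving Therapy Type term would have no second level.

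**The case against.** A reader might infer that the ANOVA cannot be run at all and that compliance has no analysis. That goes too far. With a single training value the model reduces to a comparison of VS with SE. This is the games versus exercise half of the Aim 1 hypothesis, and Section 5 also mentions comparing group means. What stands is that this remainder depends on the outcome being recorded in both groups, which the documents do not establish, and that it does not reach ME versus MnE.

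A reader might also infer that no part of the plan tests ME against MnE on compliance. The documents do not support this either. The SAP is built on an enhanced versus un-enhanced comparison, and its Table 5, which is not available here, is where such a contrast could sit. The gap is established for Protocol Section 5 only.

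Activity monitors could in principle be worn around test visits. No section says so: Aim 1 pairs them with start and stop times of practice.

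Finally, one might argue from sample size that ME versus MnE is underpowered. That is a separate question. Any detectable difference would be the same if Section 5 were written correctly, so it does not measure this defect.

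**Conclusion.** Wrong as written for a primary outcome, and to be corrected before compliance data are examined. For duration of motor activity, at least 3 of the 4 Test levels are empty, the Test and interaction terms have 0 degrees of freedom instead of 3 each, and the Month 1 versus Month 6 comparison has no data. A between-group VS versus SE comparison of one training value remains, on the condition above. Section 5 has no ME versus MnE term; that statement is limited to Section 5.

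The conclusion rests on reading Section 4.2's two-way division of the data as complete: a variable listed under daily training, and not under the testing periods, is collected only in training. Nothing elsewhere in the documents contradicts this reading. The Wolf Motor Function Test analysis is unaffected by this point.

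**What to change.** Before compliance data are examined:

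1. Remove compliance from the Test-factor ANOVA and from the Month 1 versus Month 6 comparison. Analyse one training-period value of duration of motor activity (moving time) per randomised subject, scaled to the assigned training length if that length varies. Use a between-arm linear model with a planned ME versus MnE contrast, adjusted for baseline upper-extremity Fugl-Meyer score, which is already collected and is the SAP's stratifier for assignment.
2. Add a games versus standard exercise contrast only if HBSE is randomised concurrently with ME and MnE.
3. Reconcile the compliance instruments in Protocol Sections 1 and 4.2, and name one for HBSE. Compare arms only on a measure recorded the same way in each. If software time stamps are all that games and exercise share, report that comparison as time on task, not as moving time.
4. Reconcile the arm structure and labels across Protocol Sections 1, 3, 3.3, 4.1, 4.1.1.2 and 5 and the SAP's Treatment Protocol and Subjects text. Reconcile also the training length: Protocol Section 3.1 gives three to twelve months, the SAP twelve weeks.

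The cost is wording changes and a little analysis work. The downside is that a single training-period value combines early stopping with low weekly use in one number.
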